15.19 Nursing Guidelines

- 15.191 Liver toxicity and liver failure have resulted from this agent. Monitor LFT's closely and instruct patients to report any abdominal pain, jaundice or significant fatigue to the study team. Dose reduce or interrupt treatment as per protocol.
- 15.192 Hypertension has been seen. Monitor blood pressure as outlined in protocol.
- 15.193 Instruct patient to report and rash, or signs symptoms of palmar-plantar erythrodysesthesia to study team. Rarely SJS and TENS have been seen with this agent. Instruct patients to seek immediate medical attention if they experience rash with fever, blisters, sloughing of tissue (especially in the mouth and vaginal, anal regions). Treat symptomatically and monitor for effectiveness.
- 15.194 Warn patients of possibility of alopecia.
- 15.195 Gastrointestinal side effects can include, diarrhea, nausea, vomiting, decreased appetite, weight loss, mucositis and less commonly taste changes, dry mouth, and reflux. Treat symptomatically and monitor for effectiveness.
- 15.196 Cytopenias are seen with agent. Monitor CBC w/diff and instruct patient to report signs, symptoms of infection or any unusual bruising or bleeding to the study team.
- 15.197 Secondary skin cancers have been reported. Instruct patients to report new or changing lesions to study team.
- 15.198 Reversible Posterior Leukoencephalopathy Syndrome (RPLS) is a rare (<1%) but serious condition. Presenting symptoms may include changes in mental status, visual disturbance, seizure, or other CNS changes. Patients with this syndrome generally had HTN as well, therefore BP monitoring is important. Instruct patient to report any mental status changes, visual changes, seizures, or other CNS changes to the MD immediately. These may be a sign of RPLS or more serious condition, such as hemorrhagic event in the CNS.

15.2 Clobetasol Propionate Cream (Temovate®)

15.21 Background: Clobetasol propionate cream has anti-inflammatory, antipruritic and vasoconstrictive properties. Topical corticosteroids may depress the formation, release, and activity of endogenous chemical mediators of inflammation (kinins, histamine, liposomal enzymes, prostaglandins) through the induction of phospholipase A2 inhibitor proteins (lipocortins) and sequential inhibition of the release of arachidonic acid. Clobetasol has very high range potency.

15.22 Formulation: Clobetasol propionate 0.05% cream contains clobetasol propionate 0.5 mg/g in a cream base of propylene glycol, glyceryl monostearate, cetostearyl alcohol, glyceryl stearate, PEG 100 stearate, white wax, chlorocresol, sodium citrate, citric acid monohydrate, and purified water.

15.23 Preparation and storage: Once the drug has been received it must be kept in a secure, dry location. Clobetasol propionate must be stored in its original packaging at a temperature between 15°C and 30°C (59°F and 77°F). Cream should not be refrigerated.

15.24 Administration: Apply a thin layer of clobetasol propionate cream to the palms of the hands and soles of the feet. Avoid washing hands and feet for one hour after application of clobetasol propionate cream. The use of clobetasol propionate is for external use only. Avoid contact with the eyes and mucous membranes. Do not apply to face or intertriginous areas. Do not use if there is atrophy at the treatment site. Minimize contact to nonaffected areas of the body. The treated skin should not be bandaged, otherwise covered, or wrapped so as to be occlusive unless directed by the physician.

15.25 Pharmacokinetic information:

Absorption: Percutaneous absorption is variable and dependent upon many factors including vehicle used, integrity of epidermis, dose, and use of occlusive dressings (not recommended)

Metabolism: Hepatic

Excretion: Urine and feces

15.26 Potential Drug Interactions: Due to the topical use of clobetasol propionate, drug-drug interactions are thought to be minimal.

15.27 Known potential toxicities:

Precautions:

Systemic absorption of topical corticosteroids can produce reversible HPA axis suppression with the potential for glucocorticosteroid insufficiency after withdrawal from treatment. Manifestations of Cushing syndrome, hyperglycemia, and glucosuria can also be produced in some patients by systemic absorption of topical corticosteroids while on therapy. Patients applying a topical steroid to a large surface area or to areas under occlusion should be evaluated periodically for evidence of HPA axis suppression. This may be done by using the ACTH stimulation, A.M. plasma cortisol, and urinary free cortisol tests. Patients receiving super-potent corticosteroids should not be treated for more than 2 weeks at a time, and only small areas should be treated at any one time due to the increased risk of HPA suppression.

If HPA axis suppression is noted, an attempt should be made to withdraw the drug, to reduce the frequency of application, or to substitute a less potent corticosteroid. Recovery of HPA axis function is generally prompt upon discontinuation of topical corticosteroids.

Infrequently, signs and symptoms of glucocorticosteroid insufficiency may occur that require supplemental systemic corticosteroids. For information on systemic supplementation, see prescribing information for those products. If irritation develops, clobetasol propionate cream should be discontinued and appropriate therapy instituted. Allergic contact dermatitis with corticosteroids is usually diagnosed by observing a failure to heal rather than noting a clinical exacerbation as with most topical products not containing corticosteroids. Such an observation should be corroborated with appropriate diagnostic patch testing. If concomitant skin infections are present or develop, an appropriate antifungal or antibacterial agent should be used. If a favorable response does not occur promptly, use of clobetasol propionate cream should be discontinued until the infection has been adequately controlled.

Adverse reactions, significant

Frequency not always defined; may depend upon formulation used, length of application, surface area covered, and the use of occlusive dressings.

Central nervous system: Localized burning (5% to 40%), stinging sensation (<2% to 5%), numbness of fingers (<2%), local pain (1%), intracranial hypertension (systemic effect reported in children treated with topical corticosteroids)

Dermatologic: Pruritus (<2% to 3%), eczema asteatotic (2%), erythema (<2%), folliculitis (<2%), skin atrophy (<2%), telangiectasia (<2%), xeroderma (<1% to 2%), atrophic striae (children)

Endocrine & metabolic: Adrenal suppression, Cushing's syndrome, glucosuria, growth suppression, HPA-axis suppression, hyperglycemia

Local: Skin fissure (<2%), local irritation (1%)

Respiratory: Upper respiratory tract infection (8%), nasopharyngitis (5%), streptococcal pharyngitis (1%)

<1% (Limited to important or life-threatening): Alopecia, exfoliation of skin, skin rash, urticaria

15.28 Study agent procurement:

Commercial supplies. Pharmacies or clinics shall obtain supplies from normal commercial supply chain or wholesaler.

15.29 Nursing Guidelines

15.291 As therapy is a topical preparation, side effects are expected to be minimal.

15.292 Instruct patients to apply a thin layer to palms of hands and soles of feet. Patients should be instructed not to wash these areas for a minimum of 1 hour after application.

15.293 Instruct patients to avoid contact with the eyes and mucous membranes.

15.294 Patients may experience a local burning/stinging sensation depending on the strength.

15.295 Rarely after prolonged use and discontinuation, patients may display symptomatic signs of glucocorticoid insufficiency. Instruct patients to report any excessive fatigue, facial puffiness (moon face) to the study team.

15.296 Rarely after prolonged use, patients may experience elevated glucose levels, instruct diabetics to monitor sugar levels and report any fluctuations to the study team.

16.0 Statistical Considerations and Methodology

16.1 Study Design

This is a randomized phase II study of regorafenib starting at low dose (Arm A, combining A1 and A2) compared to standard dose of regorafenib (Arm B, combining B1 and B2) in patients with refractory metastatic colorectal cancer (mCRC). Patients will be randomized 1:1:1:1 to one of the following 4 arms:

A1: Regorafenib start low dose and pre-emptive Clobetasol for PPES

A2: Regorafenib start low dose and reactive Clobetasol for PPES

B1: Standard dose of regorafenib and pre-emptive Clobetasol for PPES

B2: Standard dose of regorafenib and reactive Clobetasol for PPES

(see Schema)

16.2 Sample Size, Accrual Time and Study Duration

Accrual time is anticipated to be 18 months, with approximately 2 months of follow-up per patient until occurrence of the primary endpoint and approximately 6 months of planned follow-up overall per patient. The sample size will be 110 patients, with approximately 28 patients randomized per regorafenib and strategy treatment sub-arm (A1, A2, B1, B2). An additional 13 patients overall will be enrolled to account for drop-out, cancels, ineligibles, etc., to give a total sample size of 123 patients. The total study duration (accrual and follow-up) is expected to be approximately 2 years.

16.3 Statement for Primary Endpoint

The primary endpoint is the proportion of patients in each arm who complete 2 cycles of protocol treatment and initiate cycle 3. The proportion will be calculated among evaluable patients separately by arm (Arm A vs. Arm B). Evaluable patients are defined as patients who are eligible, consented, received any protocol treatment. In the CORRECT trial, among patients who were randomized to regorafenib, 45% continued treatment beyond cycle 2. Other than disease progression, majority of patients discontinued regorafenib due to adverse events not associated with progression. It was noted that most adverse events occurred during Cycles 1-2 of the treatment (Grothey A et. al., 2013, Lancet). Assuming 45% of patients would complete 2 cycles of protocol treatment and initiate cycle 3 in the control (standard dose; pooled arms B1 and B2) group, and desiring an improvement to 63% in the experimental (starting low dose) group (pooled arms A1 and A2), a one-sided test with $\alpha = 0.20$ and power of 80% will require a sample size of 110 patients enrolled to both regorafenib arms (A and B). We will enroll 13 additional patients to account for ineligibility, cancellation, major treatment violation, or other reasons. Maximum projected accrual is therefore 123 patients. A Fisher exact test will be used to detect a difference in proportion of patients who complete 2 cycles of protocol treatment and initiate cycle 3 between arms (starting low dose [pooled arm A1 and A2] vs. standard dose [pooled arm B1 and B2]). The proportion of patients who complete 2 cycles of protocol treatment and initiate cycle 3 will be computed by arm with its 95% confidence interval using exact method.

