1.0 Background

- 1.1 Worldwide, nearly 1.3 million patients are diagnosed with and more than 600 000 patients die from colorectal cancer every year (Ferlay et al, 2013). Regorafenib is a novel oral multikinase inhibitor that blocks the activity of several protein kinases, including kinases involved in angiogenesis, oncogenesis and tumor microenvironment (Kies et al, 2010). Regorafenib was recently shown to provide a survival benefit in metastatic colorectal cancer patients who have progressed after all standard therapies (Grothey, et al). This led to its approval in September 2012 by the FDA for use in the United States. Despite the observed benefits in a patient population with no current standard, toxicities such as Palmar-plantar erythrodysesthesia syndrome (PPES) (which occurs early in the first 1-2 weeks) and fatigue have widely limited its use in the US. Multiple practices across the US have adopted, and despite the absence of supportive data, various dosing or interval scheduling including starting at lower doses and escalate as tolerated, every other week dosing intervals and other.

In this study, we propose to design a novel strategy to optimize the dose of regorafenib in patients with refractory mCRC to allow maintenance of the observed benefits while improving the tolerability profile. The proposed strategy, arm A (combining A1 and A2) consists of starting regorafenib at 80 mg/day for 1 week (week1), then if no significant drug-related toxicities escalate to 120 mg/ day for another week (week 2), then again if no significant related toxicities escalate to a total dose of 160 mg/day (week 3) followed by a week break (week 4 of cycle 1). If at the end of week 1, week 2 or week 3 toxicities are unacceptable as defined by the study, the decision will be to deescalate by 40 mg/day and there will be no further dose escalations. A comparative arm, arm B (combining B1 and B2) will include a standard dose/schedule regorafenib of a 160 mg/day starting on day 1 of cycle 1. The primary goal of this study is to compare the proportions of patients on each arm who complete 2 cycles of protocol treatment and initiate cycle 3. We will also assess other outcome and quality of life measures and toxicity profile with a focus on regorafenib related toxicities. We will also assess a potential strategy to reduce the severity of PPES. Additionally, we will perform limited PK analysis in both arms.

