- 6.22 After the patient has been registered into the study, the patient will be assigned to one of the following treatment groups, in 1:1:1:1 fashion, using the Pocock and Simon dynamic allocation procedure which balances the marginal distributions of the stratification factors between the treatment groups (Pocock-Simon, 1975).
- Arm A 1: Regorafenib Cycle 1: 80 mg daily Week 1/120 mg daily Week 2/160 mg daily week 3 then 1 week off followed by Cycle 2+ (160 mg for 21 days/1 week off) + pre-emptive strategy for PPES starting Cycle 1 Day 1
 - Arm A 2: Regorafenib Cycle 1: 80 mg daily week 1/120 mg daily week 2/160 mg daily week 3 then 1 week off followed by Cycle 2+ (160 mg for 21 days/then 1 week off) + reactive strategy for PPES
 - Arm B 1: Regorafenib 160 mg daily for 21 days/then 1 week off + pre-emptive strategy for PPES starting Cycle 1 Day 1
 - Arm B 2: Regorafenib 160 mg daily for 21 days/then 1 week off + reactive strategy for PPES

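### Section 16.3: Fisher's exact test meets the planned 80% power but leaves part of the one-sided alpha of 0.20 unused; Boschloo's exact test would use it, for 0.0 to 4.9 points of power at 110 to 123 evaluable patients

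*Combined protocol and SAP*

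**What the plan says.** Section 16.3 assumes that 45% of patients on standard dose (pooled B1 and B2) start cycle 3 and aims for 63% on the low starting dose (pooled A1 and A2). With a one-sided alpha of 0.20, it states that "power of 80% will require a sample size of 110 patients enrolled to both regorafenib arms". The test is then named: "A Fisher exact test will be used to detect a difference in proportion of patients who complete 2 cycles of protocol treatment". That sentence does not repeat the sidedness; I read it as one-sided, in line with the sample-size sentence.

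The denominator is not fixed in advance. Section 16.3 says "Evaluable patients are defined as patients who are eligible, consented, received any protocol treatment". Section 16.2 adds a reserve: "An additional 13 patients overall will be enrolled to account for drop-out, cancels, ineligibles, etc., to give a total sample size of 123 patients". Section 6.22 assigns patients 1:1:1:1 to four arms, "using the Pocock and Simon dynamic allocation procedure which balances the marginal distributions of the stratification factors between the treatment groups". The evaluable counts in pooled A and pooled B are therefore known only after losses.

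On estimation, section 16.3 says that the proportion "will be computed by arm with its 95% confidence interval using exact method". It plans no interval for A minus B, although section 1.1 says "The primary goal of this study is to compare the proportions of patients on each arm". The plan does not state the attained size of the Fisher test, and it mentions no unconditional exact test.

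**The concern.** Fisher's test conditions on the total number of successes. With about 55 patients per arm its attainable p-values are coarse, so a nominal 0.20 test usually runs well below 0.20. The sponsor has accepted a 20% false-positive risk in exchange for a small trial. If the test delivers only about 15%, some of that exchange is not collected.

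At stake are a few points of power, and some protection if losses exceed the planned 13. The margin over 80% at 55/55 is only 0.4 point. The validity of the primary test is not in question.

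**Working it through.** **Inputs.** From section 16.3: rates 0.45 (B) and 0.63 (A), one-sided alpha 0.20, N = 110, 13 extra, 123 in all. From section 16.1: 1:1:1:1 allocation, so 1:1 for the pooled arms.

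**Formulas.** Let xA and xB be the successes among nA and nB.

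- Fisher: p(xA, xB) = P(X ≥ xA), with X hypergeometric given the total xA + xB. Reject if p ≤ 0.20.
- Power = Σ Bin(xA; nA, 0.63) × Bin(xB; nB, 0.45) over the rejected tables.
- Size at a common rate π = the same sum with both rates equal to π. Maximum size = the largest value over π.
- Boschloo: reject if p(xA, xB) ≤ c, where c is the largest cutoff whose maximum size is ≤ 0.20. Fisher's cutoff of 0.20 already meets that condition, so c is at least 0.20 and every Fisher rejection is kept.

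**Step 1: the plan's own figure.** One-sided Fisher power is 79.7% at 54 per arm and 80.4% at 55 per arm. The smallest equal-arm size reaching 80% is 55, so N = 110 is reproduced exactly. A two-sided Fisher test at 0.20 with 55 per arm has only 68.2% power, which confirms the one-sided reading.

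**Step 2: the two tests at selected counts.**

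| A/B | Power, Fisher | Power, Boschloo | Max size, Fisher | Max size, Boschloo | Size at 45%, Fisher | Size at 45%, Boschloo |
|---|---|---|---|---|---|---|
| 55/55 | 80.44% | 85.31% | 15.29% | 19.55% | 14.59% | 19.43% |
| 56/55 | 83.51% | 83.51% | 17.25% | 19.68% | 16.77% | 17.42% |
| 55/54 | 82.85% | 82.88% | 17.03% | 19.97% | 16.55% | 17.99% |
| 52/52 | 78.08% | 83.46% | 15.57% | 19.35% | 13.94% | 18.76% |

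At 55/55 the gain is 85.31 − 80.44 = 4.87, or 4.9 points. At 52/52 it is 83.46 − 78.08 = 5.38, or 5.4 points.

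**Step 3: all near-equal splits.** I enumerated every split with 103 to 123 evaluable and arms within 5, which gives 116 splits.

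- Fisher's maximum size is 15.1% to 17.3%. Boschloo's is 19.4% to just under 20.0%. No table rejected by Fisher is lost at any split.
- At 110 or more evaluable (77 splits), Fisher's minimum power is 80.2% and Boschloo's is 83.5%. The gain is 0.0 to 4.9 points, average 3.4.
- At 103 to 109 evaluable (39 splits), Fisher is below 80% at 19 (lowest 78.1%). Boschloo's minimum is 80.9%. The largest gain is 5.4 points, at 52/52.
- Average size at a 45% common rate over the 116 splits is 15.3% for Fisher and 18.7% for Boschloo.

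**Step 4: the chance of ending below 80% with Fisher.** This needs a loss rate, which the documents do not give. Assume 123 enrolled as 62/61, with independent losses:

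| Assumed loss rate | Chance that Fisher's power is below 80% |
|---|---|
| 13/123 = 10.6% | about 17% |
| 8% | 3.3% |
| 6% | 0.3% |

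**Step 5: what a win looks like.** At 55/55 with 25/55 in arm B, Fisher needs 31/55 in arm A (p = 0.170). The gap is 6/55 = 10.9 points, 95% Newcombe interval −7.6 to 28.4. Boschloo needs 30/55 (p = 0.196; Fisher p = 0.223). The gap is 5/55 = 9.1 points, interval −9.3 to 26.7.

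**The case against.** The strongest reply is that nothing needs repair. Fisher's test is valid, and the 110 patients were sized for it, so its conservatism is already paid for. The extra power is also bought almost one for one with false positives: at 55/55 power rises 4.9 points and size at 45% rises 19.43 − 14.59 = 4.8 points. At 56/55 and 55/54 the size rises while power hardly moves. With so lenient an alpha, and with survival comparisons that section 16.4 says are not powered for non-inferiority, a team may prefer an attained rate near 15%.

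All of that stands as description. It does not remove the point, because the sponsor fixed 20% as the acceptable risk and Boschloo's test stays inside it. A team that really wants 15% could choose that openly; at present it arises from the choice of test and is not stated.

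A reader might infer three stronger things, and the documents support none of them:

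- That the trial is underpowered or N is wrong. It is not: 110 is exactly right for the named test.
- That 5.4 points is the gain to expect. That figure needs a fall to 104 evaluable, which means 123 − 104 = 19 losses against the 13 planned.
- That there is a 17% risk of missing 80% power. That holds only if losses run at the full reserve rate, which centres the evaluable count on 110. At 8% or 6% loss the risk is small.

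On the interval, section 2.11 asks only for the proportion in each arm, and a difference interval can be computed from the reported counts. It is a reporting addition and does not carry this point.

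**Conclusion.** The point holds as an efficiency improvement. Fisher's test delivers the promised power at the planned numbers but uses only 15.1% to 17.3% of the 20% allowed. Boschloo's test is exact, never less powerful, and within the stated alpha. At 110 to 123 evaluable patients its benefit averages 3.4 points, depends strongly on the final split, and can be nil. Below 110 evaluable it also keeps power above 80% at all 39 splits checked, where Fisher dips to as low as 78.1%.

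These results assume the plan's own rates of 45% and 63%, a one-sided reading of the Fisher test, and pooled arms within 5 patients of each other. Only the probabilities in step 4 rest on a loss rate from outside the documents.

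**What to change.** In section 16.3, before any outcome data are seen:

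- Name Boschloo's exact test at one-sided alpha 0.20 as the primary test of pooled A vs pooled B among evaluable patients, with Fisher's exact test as a sensitivity analysis.
- Keep N = 110 plus 13, and keep the stated power as at least 80%.
- State the price: the average false-positive rate at a 45% common rate goes from 15.3% to 18.7%, still under 0.20, and at some counts it rises with almost no power gain.
- Optionally, report A minus B with a 95% Newcombe interval, labelled as an estimate and not a decision rule.

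The cost is a few lines of wording and code, with no extra patients or data. A team that prefers an attained size near 15% can keep Fisher, say so, and add only the interval.

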16.4 Supplementary Analysis Plans (includes all secondary and translational goals)

- 16.41 Overall survival (OS) is defined as time from randomization to death due to any cause. OS will be estimated with Kaplan-Meier survival curves and differences between regorafenib arms (A vs. B) tested using log-rank tests, though we note these analyses are not powered for formal non-inferiority assessments. See Section 2.21.
- 16.42 Progression-free survival (PFS) is defined as the time from randomization to the earlier of disease progression or death due to any cause, where progressed disease (PD) is as defined by RECIST 1.1 (see Section 11.0). PFS will be estimated with Kaplan-Meier survival curves and differences between regorafenib arms (A vs. B) tested using log-rank tests, though we note these analyses are not powered for formal non-inferiority assessments. See Section 2.21.
- 16.43 Time to progression (TTP) is defined as the time from randomization to disease progression, where progressed disease (PD) is defined by RECIST 1.1 (see Section 11.0). TTP will be estimated with Kaplan-Meier survival curves and differences between regorafenib arms (A vs. B) tested using log-rank tests, though we note these analyses are not powered for formal non-inferiority assessments. See Section 2.21.
- 16.44 The cumulative (total) dose of regorafenib received by patients and dose intensity in the first two cycles will be summarized with descriptive statistics and compared between regorafenib arms (A vs. B) using the t-test (if approximately normally distributed) or the Wilcoxon rank sum test (if not approximately normally distributed). Dose intensity is defined as the cumulative (total) dose of regorafenib divided by the expected total dose. See Section 2.22.
- 16.45 The proportion of patients overall and within each arm experiencing grade 3 or 4 HFS or fatigue will be computed with 95% confidence intervals, and differences between regorafenib dosing strategies (pooled across HFS strategies) tested using a Fisher Exact test. The incidence of grade 3 or 4 HFS will also be descriptively compared between those receiving a pre-specified preemptive vs. reactive approach for hand and foot syndrome (pooled across dosing strategies), and tested using a Fisher Exact test. See Section 2.24. Adverse event reports will be shared with [name] of Memorial Sloan Kettering Cancer Center 1-2 times per month for review.
- 16.46 Furthermore, patients will be descriptively compared between treatment arms and between HFS treatment strategies (pre-emptive vs. reactive) according to self-reported outcomes given on the HFS14 questionnaire. See Section 2.24. Results from the cycle 1 and 2 HSF14 questionnaires will also be summarized descriptively as they relate to the pre-emptive versus reactive PPES strategies, with comparisons made within and between arms using the t-test or Wilcoxon rank sum test as appropriate, as well as taking time-dependence into account. Changes in QOL (according to the LASA questionnaire as measured by the overall QOL question) from baseline will also be compared between the treatment arms using the t-test or Wilcoxon rank sum test. We hypothesize that patients receiving regorafenib will experience greater deficits in QOL as reflected by scores on the HSF14, the BFI and the LASA. These questionnaires have specific application to this population. See Section 2.24.
- 16.47 Pharmacokinetic Analysis
- The samples will be analyzed for the regorafenib concentrations using liquid chromatography mass spectrometry, with the anticipated method being a modified version

of that published by Van Erp et al. The samples will be analyzed for M2 and M5, if cost-free standards can be obtained from Bayer.

After quantitation, the average regorafenib concentration will be calculated by arms (Arm A vs. B) at each time point.

As exploratory analysis, this average concentration will be correlated with toxicity and efficacy endpoints. Further descriptive characteristics of the pharmacokinetics will also be calculated. An example includes (but is not limited to) within-patient variability in the trough concentrations pharmacokinetic parameters will also be calculated, both overall and within cycles, as a ratio of the maximum:minimum value.

